## **4.5 Study Drug Accountability and Compliance**

### **4.5.1 Study Drug Accountability**

The investigator or an appointed designee is responsible for ensuring that deliveries of study drug are correctly dispensed and recorded, that the product is handled and stored safely and properly, and that it is only given to subjects in accordance with this protocol.

Sites will keep a current log of drug accountability recording:

- What drug supply was received from the sponsor
- What drug supply was dispensed to each subject
- What drug supply is current in inventory
- What drug supply was destroyed or returned to the sponsor for destruction

Note: Drug accountability is the responsibility of the investigator; a written account will be required for all discrepancies.

If the study drug supplies appear to be damaged/missing upon arrival at the investigational site, the sponsor should be contacted immediately.

The sponsor's designated monitor must verify all accountability records during periodic monitoring visits. Unused and used study drug must be stored on site until such accountability has taken place and authorization is received from the sponsor or sponsor's designee that the study drug may be returned or destroyed.

### **4.5.2 Subject Compliance with Study Drug**

Compliance will be assessed by capsule counts. Subjects will be instructed to bring all used empty bottles and unused study drug with them to the clinic visit on Day 26.

## 4.6 Dose Adjustments / Toxicity Management

Adverse events will be graded for intensity by the investigator (see [Section 10.2.2.2](#)).

Dosing will be discontinued for all study drug-related SAEs.

A member of the study staff will contact any subject who is suspected of experiencing neuropsychiatric AEs to determine the need for an unscheduled visit before further dose escalation may proceed. Subjects who are experiencing any AEs may also be asked to return for an unscheduled visit. Subjects who are suspected of experiencing a neuropsychiatric event should be seen in person.

In all subjects with intolerable AEs (as defined in [Section 10.2.1](#)) that are considered related to study drug, treatment should be suspended for up to 48 hours or until the AE resolves to a tolerable level of severity, whichever is earlier. In subjects who are unable to tolerate 6 mg BID, 8 mg BID or 10 mg BID, dosing may then be resumed at a previously tolerated lower dose. Only a single dose-step reduction (i.e., 10 mg BID to 8 mg BID, 8 mg BID to 6 mg BID, or 6 mg BID to 4 mg BID) is permitted. Reescalation of the dose is NOT permitted. Dosing should be discontinued if there is recurrence of intolerable AEs after the dose reduction. Subjects who experience intolerable AEs while receiving the 2 mg BID or 4 mg BID dose will be discontinued from treatment. Table 2 details dose reductions by dose level.

**Table 2 Study Drug Dose Reduction for Intolerable AEs**

Dose and Schedule of Study Drug	Dose Reduction
2 mg BID	Remove from treatment 
4 mg BID	Remove from treatment
6 mg BID	4 mg BID
8 mg BID	6 mg BID
10 mg BID	8 mg BID

1 – Subjects who are removed from treatment for AE(s) should be followed for resolution of the AE(s) and should complete all assessments scheduled for the End-of Study (EOS)/Follow-up (FU) Visit, as well as all assessments that they are capable of completing on the scheduled visit day if the decision to remove from treatment is made on a scheduled visit day. Likewise, if the investigator plans to temporarily interrupt dosing because of an AE and the decision is made on a scheduled visit day, then the subject should complete all scheduled assessments that they are capable of completing on the visit day on which they appear.

All subjects who discontinue treatment due to AEs will be followed for AE outcome. All AEs should be followed for resolution or for 30 days from the last dose of study drug, whichever is shorter.

The Study Safety Representative should be notified of all dose reductions as soon as is feasible.

All subjects who discontinue treatment due to AEs will be followed for AE outcome. All AEs should be followed for resolution or for 30 days from the last dose of study drug, whichever is shorter.

## 4.7 Overdose Management

To date, no overdoses of CX-8998 in humans have occurred. Therefore, specific information regarding treatment of overdose is not currently available. In case of an acute overdose, it is recommended that the stomach be emptied and oral gavage with activated charcoal be used to help

reduce absorption of CX-8998. In the event of an overdose, the Study Safety Representative should be contacted immediately.

## **5 INVESTIGATORS, SITES, AND DURATION**

### **5.1 Investigators and Sites**

The study will be conducted at multiple sites in the United States.

### **5.2 Central Reviewers**

A central reviewer and the sponsor will review eligibility criteria for all subjects. The site will submit an eligibility checklist for evaluation of each subject. No subject may be enrolled or receive study drug prior to receipt of notification that the central reviewer and review process have deemed the subject eligible.

### **5.3 Duration of Study**

Subjects will participate for a total of up to 9 weeks, including screening, the 4-week treatment period, and follow-up.

### **5.4 Termination of Study**

This study may be terminated at the discretion of the sponsor or the Food and Drug Administration (FDA) or in accordance with the recommendations set forth in the Safety Monitoring Plan ([Section 10.4](#)).

## **6 STUDY POPULATION**

### **6.1 Number of Subjects**

Up to approximately 15 eligible subjects will receive treatment.

### **6.2 Inclusion Criteria**

Subjects may be included in the study only if they meet all of the following criteria. Subjects may undergo rescreening following consultation with and approval of the Study Safety Representative.

- 1) Signed informed consent form (ICF) indicating that the subject has been informed of the procedures to be followed, the experimental nature of the therapy, alternatives, potential benefits, side effects, risks, and discomforts.
- 2) Men or nonpregnant, non-breastfeeding women 16 to 55 years of age who are able to read and understand the written and spoken local language.
- 3) Clinical diagnosis of IGE (including, but not limited to, CAE, JAE, juvenile myoclonic epilepsy, or Jeavons syndrome) with absence seizures consistent with the International League against Epilepsy Revised Classification of Seizures (2017).
- 4) Absence seizures, by history on average once per hour, persisting despite standard of care (SOC) treatment, defined as treatment with at least 2 AEDs appropriate for the patient's epilepsy syndrome. SOC failure, per investigator discretion, will be defined as insufficient clinical response or intolerable side effects, which precludes use of the appropriate AED.

- 5) Observation of at least 1 provoked absence seizure during at least 1 of the hyperventilation (HV) periods and at least 3 absence seizures during the 6.5-hour video-EEG. Absence seizures are defined on EEG as typical generalized 3-Hz spike and wave lasting  $\geq 3$  seconds during wakefulness. Hyperventilation should be carried out in the following manner: 5 minutes of HV (HV period 1), followed by 5 minutes of relaxation, followed by a second 5 minutes of HV (HV period 2). Subjects who have an induced seizure during HV period 1 do not need to undergo HV period 2. At least 75% of the background should be normal.
- 6) On stable doses of one or more antiepileptic medication(s) for at least 30 days. If a subject is not on medication, adequate documentation justifying lack of therapy may be acceptable for the subject after sponsor review. Ketogenic, modified Atkins diet (MAD), or low glycemic diet with stable carbohydrate ratio for at least 30 days before screening is an acceptable antiepileptic therapy. Vagal nerve stimulation at stable settings (for at least 30 days before screening), without use of the magnet, is also acceptable.
- 7) Body weight  $\geq 45$  kg at screening.
- 8) Subjects with reproductive capability, including all males and WOCBP, must agree to practice continuous abstinence or adequate contraception methods (appropriate double barrier method or oral, patch, implant, or injectable contraception) from as soon as feasible during screening period until at least 30 days after the last dose (i.e., intermittent abstinence based on "rhythm," temperature monitoring, or other means of timing is not acceptable). WOCBP include any woman who has experienced menarche and who has not undergone successful surgical sterilization (hysterectomy, bilateral tubal ligation, and/or bilateral oophorectomy) or is not postmenopausal. Postmenopausal is defined as amenorrhea for  $\geq 12$  consecutive months without another cause, and a documented serum follicle stimulating hormone (FSH) level  $\geq 35$  mIU/mL.
- 9) Male subjects with a partner of childbearing potential must be surgically sterilized or be willing to use condoms with spermicide from as soon as feasible during screening period until at least 30 days after the last dose.
- 10) Able and willing to comply with scheduled visits, treatment plan, laboratory tests, and other study procedures.
- 11) Approval by the sponsor medical personnel or delegate as to final eligibility for the study.

### **6.3 Exclusion Criteria**

Subjects will be excluded from the study if any of the following conditions apply. Subjects may undergo rescreening following consultation with and approval of the Study Safety Representative.

- 1) History of surgical intervention for treatment of epilepsy.
- 2) Additional seizure (clinical and electrographic) types, including, but not limited to, epileptic spasms, generalized tonic seizures, atonic seizures, or focal seizures. Subjects with GTCS or myoclonic seizures are eligible for the study.
- 3) Inadequately treated psychotic or mood disorder (e.g., schizophrenia, major depression, bipolar disorder).
- 4) Presence of severe intellectual disability, severe autism spectrum disorder, or severe developmental disorder such that the subject cannot sign the ICF or cannot cooperate with the study procedures.

- 5) Presence of positive urine drug screen for drugs of abuse, except if this is explained by use of an allowed prescription medicine.
- 6) Regular use of more than 2 standard drinks of alcohol per day (28 grams of pure alcohol).
- 7) Hypersensitivity/allergic reaction to other T-type calcium agents, such as (but not limited to) ethosuximide and zonisamide.
- 8) Use of strong CYP3A4 inhibitors, including prescription or nonprescription drugs or other products (e.g., grapefruit juice), which cannot be discontinued at least 2 weeks prior to Day 1 of dosing and throughout the study ([Appendix B](#)).
- 9) Concurrent illnesses that would be a contraindication to trial participation, including, but not limited to:
  - a) Severe arterial thromboembolic events (myocardial infarction, unstable angina pectoris, stroke) less than 6 months before screening.
  - b) New York Heart Association (NYHA) Class III or IV congestive heart failure, ventricular arrhythmias or uncontrolled blood pressure.
  - c) Clinically significant ECG abnormality per the investigator assessment or any of the following:
    - i. QTcF  $\geq$ 450 msec (males) or  $\geq$ 470 msec (females).
    - ii. PR interval  $\geq$ 250 msec.
    - iii. Atrioventricular block of second degree or higher, including Mobitz I.
    - iv. Persistent sinus bradycardia of  $\leq$ 50 beats per minute; persistent means the bradycardia is present on the first ECG and on one repeat ECG performed on another day.
    - v. For other ECG findings (e.g., including, but not necessarily limited to, tachycardia, bundle branch block, frequent ectopic beats) the investigator should send a scanned, identity-blinded copy of the ECG tracing to the Study Safety Representative for review.
- 10) Positive result for human immunodeficiency virus (HIV), hepatitis B [indicating ongoing infection], or hepatitis C at screening or otherwise known ongoing infection with HIV, hepatitis B, or hepatitis C, unless curative therapy has been completed; for hepatitis C curative therapy is defined as negative polymerase chain reaction (PCR) for hepatitis C virus (HCV) RNA.
- 11) Significant hepatic (AST/ALT or bilirubin  $\geq$ 2  $\times$  ULN) or renal disease (creatinine clearance  $\leq$ 39 mL/min).
- 12) History of alcohol or substance abuse within the last year.
- 13) A current C-SSRS score of 4 or 5 at screening or history of suicide attempt.
- 14) Psychological, social, familial, or geographical reasons that would hinder or prevent compliance with the requirements of the protocol or compromise the informed consent process.

- 15) Any other condition and/or situation that causes the investigator or Study Safety Representative to deem a subject unsuitable for the study (including, but not limited to, expected study medication noncompliance, inability to medically tolerate the study procedures, or a subject's unwillingness to comply with study-related procedures)
- 16) Treatment with an investigational agent within 30 days prior to the first dose of CX-8998 or planning to receive an investigational agent during the study.
- 17) Subjects who do not experience a provoked absence seizure during either HV period and who have fewer than 3 typical absence seizures during the baseline video-EEG (considered to be screen failures).

## **6.4 Withdrawal of Subjects and/or Discontinuation of Treatment**

A subject should be withdrawn from the study for any of the following:

- 1) Withdrawal of subject consent.
- 2) Subject is lost to follow-up.
- 3) Investigator determines that withdrawal from the study is in the best interest of the subject.
- 4) Subject is noncompliant with protocol-mandated activities.
- 5) Occurrence of any intercurrent condition, injury, or disease that becomes apparent during the study and necessitates the termination of the subject from the study.
- 6) Administrative reason (e.g., termination of the clinical study by a regulatory agency or the sponsor).

A subject should be discontinued from treatment for any of the following (see also [Section 4.4](#)):

- 1) Occurrence of defined unacceptable toxicity ([Section 4.6](#)).
- 2) Investigator determines that discontinuation of treatment is in the best interest of the subject.
- 3) Occurrence of any intercurrent condition, injury, or disease that becomes apparent during the study and necessitates the discontinuation of treatment.
- 4) Pregnancy.
- 5) Subjects who answer "yes" to Suicidal Ideation item 4 or 5 on the C-SSRS during the study must be withdrawn from the study treatment. Investigators should also withdraw subjects from treatment if, in the judgment of the investigator, the subject develops other indicators of significant risk of suicide. In the event that suicidal ideation is observed in any study subject, the investigator will manage the situation as he/she deems medically and psychiatrically appropriate.

### **6.4.1 Follow-up Procedures for Subjects Who Withdraw/Discontinue Prematurely**

If a subject withdraws from the study, attempts should be made to contact the subject to determine the reason(s) for discontinuation. If a subject does not return to the clinic for follow-up visits, attempts should be made to contact the subject via phone, email, or mail. At least 3 documented attempts (one of which should be a certified letter) should be made to contact the subject before declaring a subject lost to follow-up. The Study Safety Representative must be informed as soon as possible if a subject discontinues or withdraws early.

The date and the reason for study drug discontinuation or subject withdrawal from the study must be recorded on the case report form (CRF). In case of early discontinuation or withdrawal of a subject, every effort must be made to report all study-mandated observations up to the time of discontinuation/withdrawal as completely as possible.

Subjects who are removed from treatment for AE(s) should be followed for resolution of the AE(s) (see [Section 10.2.3](#)) and should complete all assessments scheduled for the End-of-Study (EOS) Visit, as well as all assessments that they are capable of completing on the scheduled visit day if the decision to remove from treatment is made on a scheduled visit day. Likewise, if the investigator plans to temporarily interrupt dosing because of an AE and the decision is made on a scheduled visit day, the subject should complete all scheduled assessments that they are capable of completing on the visit day on which they appear.

If the reason for discontinuation/withdrawal is medical and the subject has not withdrawn consent, the subject should remain under the supervision of the investigator until the medical issue is resolved or otherwise declared stable.

#### **6.4.2 Procedures for Replacing Subjects Who Withdraw/Discontinue Prematurely**

Subjects who withdraw from the study or discontinue treatment prematurely will not be replaced.

## **7 TREATMENT PLAN AND METHODS**

### **7.1 Schedule of Assessments**

The schedule of assessments is presented in [Table 3](#).

**Table 3 Schedule of Assessments**

Visit	Screening	Dosing Period										EOT	EOS	FU	
		Day	-28 to -1	1	2	3-7	8	9-13	14	15-19	20	21-25			
Visit Window			-	0		-2 d		-2 d		-2 d			±1 d	±1 d	±2 d
CX-8998 daily dose	-		4 mg		8 mg		12 mg		16 mg		20 mg				
Clinic visit	X	X										X 			
Telephone call 				X		X 		X 		X 			X 	X	
Informed consent 	X														
Demography/medical history 	X														
Eligibility criteria	X	X													
Complete physical exam	X											X			
Targeted physical exam 		X													
Neurological exam	X											X			
Vital signs 	X	X										X			
Electrocardiogram 	X	X										X			
Clinical laboratory tests 	X	X										X			
Urine (+/- serum) pregnancy test 	X											X			
Serum FSH 	X														
Drug screening 	X											X			
Pharmacogenomics sample 		X													
Blood sampling for PK 		X										X			
Video EEG + HV and PS 	X											X			
Video-EEG 	X											X			
Seizure-related Disability Assessment Scale		X										X			

Visit	Screening	Dosing Period										EOT	EOS	FU
Day	-28 to -1	1	2	3-7	8	9-13	14	15-19	20	21-25	26	33	57	
Visit Window		-	0		-2 d		-2 d		-2 d		±1 d	±1 d	±2 d	
CX-8998 daily dose	-	4 mg		8 mg		12 mg		16 mg		20 mg				
Clinic visit	X	X									X 			
Telephone call 			X		X 		X 		X 			X 	X	
Daily Seizure Diary	X	X	X	X	X	X	X	X	X	X				
C-SSRS 	X	X									X			
UM-PDHQ 		As needed												
Prior / concomitant meds	X	X			X		X		X		X			
AE review 		X			X		X		X		X	X	X 	
Study drug admin. in clinic		X 									X 			
Study drug admin. outpatient		X 	X	X	X	X	X	X	X	X	X 			
Drug compliance											X 			

AE = adverse event; C-SSRS = Columbia-Suicide Severity Rating Scale; ECG = electrocardiogram; EEG = electroencephalogram; EOS = end of study; EOT = end of treatment; FSH = follicle-stimulating hormone; FU = follow-up; HIV = human immunodeficiency virus; HV = hyperventilation, PK = pharmacokinetic;

PS = photic stimulation; UM-PDHQ – University of Miami Parkinson’s Disease Hallucinations Questionnaire.

1. Visit window ± 1 day as needed for scheduling.
2. Visit window +0, -2 days as need for scheduling.
3. Before initiating dose escalation, study staff will contact the subjects by telephone and will question them about their health status, including about the occurrence of any AEs. Subjects who report AEs may be asked to return to the clinic for an unscheduled visit. Subjects who are suspected of experiencing a neuropsychiatric event should be seen in person.
4. Informed consent must be signed prior to initiation of all other screening procedures.
5. Medical history will include seizure history.
6. A targeted physical exam will be based on subject reports of signs and symptoms and investigator’s observations.
7. Vital signs include body temperature, systolic and diastolic blood pressures, pulse rate and respiration rate. Vital signs will be collected predose and postdose (1-2 hours) at the Baseline (Day 1) Visit and during the Day 26 clinic visit. Blood pressure and pulse rate will be measured in the recumbent position after at least 2 minutes of recumbency, and both will be measured again after approximately no less than 1 minute of standing.
8. At baseline (Day 1), a 12-lead ECG will be performed predose and approximately 1-2 hours after the dose as convenient between other required visit procedures. All ECGs should be performed after at least 10 minutes of recumbency.

9. Clinical chemistry, and hematology. Urinalysis to be performed only as clinically indicated. Additional lab tests are obtained at the screening visit to verify eligibility (including HIV, hepatitis B and C). A positive drug screen will result in exclusion from the study unless it is explained by use of an allowed prescription medication.
10. A urine pregnancy test will be performed, and if the result is positive a serum pregnancy test should be completed.
11. Serum FSH only as needed to determine menopausal status in females <62 years old with history of ≥12 months of amenorrhea without another cause.
12. Laboratory urine testing for phencyclidine (PCP), cocaine, cannabinoids, opiates, barbiturates, benzodiazepines, amphetamines, methadone, and MDMA (Ecstasy).
13. Optional sample that requires additional informed consent.
14. On Day 1, PK samples will be taken at time 0 (predose; before subject takes first dose of study drug in the clinic) and at 1, 2, and 4 hours after administration of study drug. Two postdose PK samples, separated by >2 hours, will be obtained on Day 26. The time of the last dose of study drug and the time of the blood draw will be recorded.
15. A standard multi-lead 6.5-hour video EEG will be obtained using HV and PS. The first 30 minutes will consist of HV and PS. For HV, subjects will be hyperventilated for 5 minutes or until the subject has an absence seizure (HV period 1). If no absence seizure occurs during HV period 1, the subject will rest for 5 minutes and then perform hyperventilation for an additional 5 minutes (HV period 2). Photic stimulation will be performed as described in the EEG charter. The EEG will be centrally evaluated by a qualified rater.
16. After completion of the above 30-minute video-EEG during which HV and PS are conducted, the video-EEG will continue, and the subjects will be monitored during wakefulness for an additional 6 hours. The EEG recording will be centrally evaluated by a qualified rater.
17. The “Lifetime” version of the C-SSRS will be used at screening, and the “Since Last Visit” version will be completed at all other visits.
18. The UM-PDHQ is a 20-item clinician-administered questionnaire that quantitatively and qualitatively assesses hallucinations. The UM-PDHQ will be completed for any subject who reports hallucinations.
19. All AEs, irrespective of the relatedness to the study drug, will be captured from the time the ICF is signed through the EOS visit. All AEs should be followed until resolution, for 30 days after onset, for 30 days after the last dose of study drug, until the subject is lost to follow-up (as defined in [Section 6.4.1](#)), or the subject withdraws consent, whichever occurs first. Serious adverse events (SAEs) will be reported up to 30 days after the last dose of study drug. A follow-up phone call will be made 30 days after the last dose of study drug for evaluation of any SAEs.
20. Study drug will be administered in the clinic on the morning of Day 1. Study drug will be administered on an outpatient basis on the evening of Day 1 through the morning of Day 26. Subjects will be instructed to bring all used empty bottles and unused study drug, with them to the end-of-study visit on Day 26.
21. Drug compliance will be assessed by capsule count.

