**Pharmacokinetic Variables and Endpoints:**

Plasma concentrations of CX-8998 and its metabolites (including, but not limited to, M01 and M02) will be determined at various visits and doses of CX-8998. Concentrations will also be incorporated into a population PK/PD model that will estimate peak exposure ( $C_{max}$ ) and overall exposure ( $AUC$ ) of CX-8998.

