#### **3.3.2 Secondary Endpoints**

- Plasma PK parameters:  $C_{\max}$ ,  $T_{\max}$ ,  $C_{\min}$ , and partial  $AUC_{0-4h}$  for CX-8998 and metabolites (including, but not limited to, M01 and M02)
- Additional CX-8998 PK parameters ( $CL/F$ ,  $V_z/F$ ,  $t_{1/2}$ ) may be estimated, pending performance of a population PK analysis with data pooled from several studies (to be reported separately from the clinical study report).

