#### **3.3.3 Exploratory Endpoints**

- Change in frequency (number of seizures per hour) of absence seizures as defined by a 3-Hz spike and wave lasting  $\geq 3$  seconds as determined by HV (HV period 1 + HV period 2)
- Change in frequency (number of seizures per hour) of absence seizures as defined by 3-Hz spike and wave lasting  $\geq 3$  seconds during wakefulness as determined by 6.5-hour video-EEG
- Time to absence seizure occurrence during HV (HV period 1 + HV period 2)
- Percent of subjects with a shift in occurrence of absence seizure during HV (e.g., shift for seizure occurring in HV period 1 or HV period 2 to no seizures occurring during either HV period; shift from absence seizure occurring to HV period 1 to HV period 2)
- Change from baseline to end of treatment in absence seizure-free days based on seizure diary
- Absence of photic response in subjects who had photic response during the baseline video-EEG

- Change in the Seizure-related Disability Assessment Scale (SERDAS)
- Relationship between the EEG parameters and the PK of CX-8998
- Exposure-response and exposure-safety relationships using plasma concentrations of CX-8998 and its 2 primary metabolites (M01 and M02) in population PK/PD analyses (to be reported separately from the clinical study report)

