#### **7.2.8      End of Study Visit (Day 26)**

Subjects will return to the clinic for the final visit assessments detailed in [Table 3](#). This visit may take place on Day 25, 26, or 27 as needed for scheduling. Subjects will be instructed to take their dose of study drug before reporting to the clinic.

A standard multi-lead video-EEG with HV and photic stimulation (PS) will be obtained over 30 minutes and will be followed by an additional 6-hour awake video-EEG (total, 6.5 hours). During this time, safety assessments, as shown in Table 3, will be conducted, and 2 PK blood samples, separated by >2 hours, will be obtained. Subjects will undergo HV for 5 minutes (HV period 1). If no absence seizure occurs, after a 5-minute rest, subjects will undergo HV for an additional 5 minutes (HV period 2). Further details, including procedures for HV and PS will be elaborated in the EEG Charter. Adverse events that are unresolved at the visit will continue to be followed by study staff as detailed in [Section 10.2.3](#).

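### The current protocol lists Cmin as a secondary endpoint but schedules no on-treatment predose sample, and its Day 26 draws are fixed neither to a time after dose nor to the hyperventilation block

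*Protocol*

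**What the plan says.** **Endpoints.** Protocol 3.3.2 lists "Plasma PK parameters" for the parent drug and its metabolites: Cmax, Tmax, Cmin and partial AUC0-4h. It gives no day or dose for any of them. Section 3.3.3 adds an exploratory endpoint: "Relationship between the EEG parameters and the PK of CX-8998".

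**Day 1 sampling (Table 3, footnote 14).** "On Day 1, PK samples will be taken at time 0 (predose; before subject takes first dose of study drug in the clinic"), then at 1, 2 and 4 h. The Day 1 dose is 2 mg.

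**Day 26 sampling (footnote 14).** "Two postdose PK samples, separated by >2 hours, will be obtained on Day 26". Section 7.2.8 places them in the video-EEG session: "During this time, safety assessments, as shown in Table 3, will be conducted, and 2 PK blood samples, separated by >2 hours". It also says: "Subjects will be instructed to take their dose of study drug before reporting to the clinic". Footnote 14 adds: "The time of the last dose of study drug and the time of the blood draw will be recorded".

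**EEG.** Footnote 15 puts HV and photic stimulation in the first 30 minutes of the 6.5-hour recording.

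**Modelling and detail held elsewhere.** The synopsis says: "Concentrations will also be incorporated into a population PK/PD model that will estimate peak exposure" (Cmax) and overall exposure (AUC). Cmin is not named there. Section 9.1 leaves sample timing to the Laboratory Manual, which was not supplied.

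**SAP.** Section 1.1 says no subject enrolled under amendments 4 and 5 and that the amendment 3 schedule is used. In that schedule (1.2, footnotes 14 and 21) PK samples are predose, 2 h and 4 h, with in-clinic dosing on Days 1 and 26. Section 5.4 plans concentration summaries only, and Section 7 lists the EEG-PK relationship among the endpoints not to be summarized.

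**The concern.** A listed endpoint should have a sample that can measure it. Cmin at steady state needs a draw just before a dose, and the current protocol appears to have none once the subject has received drug. AUC0-4h needs a value at or near time 0 and at about 4 h, and only Day 1 has that. Fed dosing is required (4.3). The only fed Tmax visible in the documents is 4 h (Appendix D, Study PN001, a 1 mg comparison), and Day 1 sampling stops at 4 h. A highest value at 4 h therefore cannot be told from a curve that is still rising.

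The Day 26 draws also have to serve the EEG-PK endpoint, yet nothing visible ties either of them to the HV block. Section 9.2 summarises concentrations by visit, time point and dose. With no nominal time point on Day 26, values from different post-dose hours would share one row.

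If the design were used as written, one secondary endpoint would have no observed value, others would describe only the first 2 mg dose without saying so, and the HV response could lack a matching concentration.

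**Working it through.** The plan gives no figure to reproduce here; the sample size is not based on statistical considerations (11.3). Steps 1 to 3 need no PK model.

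**1. Count the draws (footnote 14, 7.2.8).**

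| Draw | Dose state | On-treatment trough? |
|---|---|---|
| Day 1, 0 h | before any drug | No |
| Day 1, 1, 2 and 4 h | after first 2 mg dose | No |
| Day 26, two draws | postdose, dose taken before arrival | No |

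There are 6 draws in all and 0 on-treatment troughs.

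**2. AUC0-4h at 10 mg.** With no time-0 sample, two draws at a and b hours bracket (min(b, 4) − a)/4 of the interval.
- 1.5 and 4 h: (4 − 1.5)/4 = 62.5%
- 3 and 6 h: (4 − 3)/4 = 25%

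Only Day 1 (0, 1, 2, 4 h) spans the interval, at one fifth of the 10 mg dose.

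**3. Chance of a draw in the HV/PS block.** Let the EEG run from 0 to 6.5 h, with draws at s and t and t − s > 2. Assume every permitted pair is equally likely.
- All permitted pairs: (6.5 − 2)²/2 = 10.125
- Pairs with s ≤ 0.5: 0.5 × 4.5 − 0.5²/2 = 2.125
- Share: 2.125/10.125 = 0.21

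So about 21% would have a draw in the block and 79% would not. The first draw can fall as late as 6.5 − 2 = 4.5 h after the EEG starts, which is 4.0 h after the block ends.

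**4. Illustrative size.** This assumes a one-compartment model at steady state with τ = 12 h and half-life 9.7 to 13.2 h (Study PN001). Here k = ln 2/t½, and ka is solved from ln(ka/k)/(ka − k) = 4, which gives 0.61 to 0.70 per hour.

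C(t) ∝ ka/(ka − k) × [e^(−kt)/(1 − e^(−kτ)) − e^(−ka·t)/(1 − e^(−ka·τ))]

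| Quantity | t½ 9.7 h | t½ 13.2 h |
|---|---|---|
| Peak/trough | 1.68 | 1.50 |
| C(6.5 h)/trough | 1.46 | 1.33 |
| C(8.5 h)/trough | 1.28 | 1.20 |
| C(1 h), % of peak | 86 | 90 |
| C(5.5 h), % of peak | 92 | 93 |
| C(7.5 h), % of peak | 81 | 84 |

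A draw 6.5 to 8.5 h after dose is thus still 1.20 to 1.46 times the trough and cannot stand in for Cmin. The bracketed parts in step 2 hold about 65% (1.5 and 4 h) and 26-27% (3 and 6 h) of the true AUC0-4h.

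For HV, suppose the EEG starts about 1 h after dose. It then ends by about 7.5 h; the latest first draw is at about 5.5 h and the latest second draw at about 7.5 h. Against 86-90% of peak at HV, those draws differ by about 3 to 6 percentage points. A draw near the peak differs by at most about 100 − 86 = 14 points.

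Study PN001 reports biphasic elimination, and its 4 h fed Tmax comes from a 1 mg single dose, so this step gives order of magnitude only.

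**The case against.** Several points on the other side stand.

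- A reader might infer that the Day 26 draws float free of both dose and EEG. They do not. Section 7.2.8 puts them within the recording, and footnote 14 makes them postdose with dose and draw times recorded. They are concurrent with the 6.5-hour seizure count, so only the HV/PS measures can lack a matching draw.
- The Laboratory Manual (9.1) may set hours. It could not add a predose draw on Day 26 without contradicting footnote 14 and 7.2.8.
- Two sparse samples with recorded times are usable input to the population model, which is stated to estimate Cmax and AUC. Cmin is not among its stated outputs, and the results are reported separately.
- Section 3.3.2 does not require AUC0-4h at the target dose, and Day 1 provides it at 2 mg.
- A reader might infer that no treated subject has a trough sample scheduled. The SAP does not support that: nobody enrolled under amendments 4 and 5, and the amendment 3 schedule includes a predose sample at both PK visits.
- A large HV mismatch is also tempting to infer. Step 4 shows it is modest at permitted draw times, and the EEG-PK endpoint is exploratory and will not be summarized.

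The missing trough remains after all of this, as does the lack of a stated day and method for each PK parameter.

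**Conclusion.** The point holds for the current protocol text. Cmin is a secondary endpoint with no on-treatment predose sample scheduled, which follows from the sampling schedule alone. Observed AUC0-4h exists only on Day 1 at 2 mg, and observed Day 1 Tmax cannot exceed 4 h. A concentration at HV is not assured: about 21% of subjects would have one if permitted draw times were equally likely, and the true share depends on site practice and on the unseen Laboratory Manual.

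The consequence is limited. This is a study of up to about 15 subjects with no formal hypotheses, and a population model can use the recorded times. The documents do not support the view that collected data are compromised, because the schedule the SAP applies has predose, 2 h and 4 h samples. The gap matters if the current protocol is used or reused.

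**What to change.** **Draw times.** In footnote 14, 4.3 and 7.2.8, keep two Day 26 draws. Take draw 1 directly after the 30-minute HV/PS block and draw 2 at the end of the awake EEG. Record the time since the last dose for each.

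**Endpoints.** In 3.3.2, state that observed Cmax, Tmax and AUC0-4h are Day 1 (2 mg) values, and flag subjects whose highest value is the 4 h sample. For Cmin and steady-state exposure, choose one:
- assign them to the population PK model and add Cmin to its stated outputs; or
- schedule a Day 26 predose draw, which either replaces one of the two draws or adds a third.

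**Reconcile.** Table 3 marks in-clinic dosing on Day 26, while footnote 20 and 7.2.8 have that morning's dose taken outside the clinic. The visit window runs from Day 25 to Day 27, but 4.3 schedules no dose on Day 27. These passages must agree on when the dose is taken relative to the visit; which is right is for the sponsor to settle.

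**Cost.** The first option is protocol wording only, with the same visits and number of draws. Sites lose some freedom in draw timing, and the list of observed PK parameters becomes shorter. It does not yield an observed trough or a 0-4 h profile at 10 mg; it makes the endpoint list match what the schedule can deliver.
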